
Study intervention Assignment
	
 
● Approximately 320 participants will be randomized in a 2:1 ratio, in favor of Arm 1. Arm 1 (single agent belantamab mafodotin) will enroll approximately 214 participants and Arm 2 (pom/dex) will enroll approximately 106 participants. Participants will be stratified based on the following: previous treatment with anti-CD38 (Y/N), with a 40% global enrolment cap for participants with prior anti-CD38 treatment, stage (International Staging System [ISS]) (I/II or III), and number of prior lines of therapy (<math>\leq 3</math> vs <math>> 3</math>), with a 55%
 

Overview of Study Design and Key Features			
	global enrolment cap for participants with $\leq 3$ prior lines. No cross-over will be allowed until final OS analysis.		
Analysis	Analyses Timing from Randomization	Planned PFS analyses	Planned OS analyses
	~25 months	PFS final Approximately 151 PFS events and the first 320 randomized subjects have been followed for a minimum of 4 months c	OS IA for efficacy a ~100 OS events ~40% OS info
	48 months	N/A	OS IA for efficacy b ~175 OS events ~70% OS info
	>60 months	N/A	OS final b ~250 OS events
	a. Provided that final PFS analysis is significant. b. If PFS is significant and null hypothesis is not rejected at the 2 nd OS IA for efficacy. c. First dose of 320 th subject happens around 21 months		

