- A high score for functional scales and for Global Health Status/QoL and summary score represent better functioning ability or Health-Related Quality of Life (HRQoL), (higher score indicates improvement)
- whereas a high score for symptom scales and single items represents significant symptomatology [Proskorovsky, 2014]. (lower score indicates improvement)

Descriptive summaries (mean, SD, median, min and max) of the actual value and change from baseline at selected time points will be provided for EORTC QLQ-C30 summary score and each domain score. The number and percentage of participants with post-baseline score improved by  $\geq 10$ , and  $\geq 5$  points, respectively from baseline score will be summarized at selected time points. The number and percentage will be provided for summary score and each domain score. Should new thresholds be available at the time of the analysis (i.e. from ongoing EORTC group work) these modified thresholds will be used and specified in OPS.

Plots of mean change from baseline (including baseline) and 95% confidence interval over time by visit, and at end of study treatment, last follow-up, and worst case post-baseline for individual domain score and summary scores will also be provided.

Longitudinal changes from baseline by treatment group for EORTC QLQ-C30 domain Fatigue will be explored using a restricted maximum likelihood-based mixed model for repeated measures (MMRM) to compare between-treatment difference adjusting for correlations across multiple time points within a patient and controlling for the baseline value. Adjusted mean difference and 95% CIs will be presented to illustrate the effect of treatment.

The MMRM model will include patient, treatment, analysis visit, and treatment-by-visit interaction as explanatory variables, the baseline value as a covariate along with the baseline-by-visit interaction. Treatment, visit, and treatment-by-visit interactions will be fixed effects in the model; patient will be treated as a random effect. An unstructured

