covariance matrix will be used to model the within subject variance and the Kenward-Roger approximation will be used to estimate the degrees of freedom. Restricted maximum likelihood (REML) estimation will be used. If the fit of the unstructured covariance structure fails to converge, the following covariance structures will be used in order until convergence is reached: toeplitz with heterogeneity (TOEPH), autoregressive with heterogeneity (ARH(1)), Toeplitz (TOEP), and autoregressive (AR(1)). If there are still issues with the fit of the model or estimation of the treatment effects, SUBJECT will be treated as a fixed effect.

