Longitudinal changes from baseline by treatment group for EORTC QLQ-IL52 domain score will be explored using a restricted maximum likelihood-based mixed model for repeated measures (MMRM), using the same approach described in Section for EORTC QLQ-C30 analysis.

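### The last fallback of the PRO mixed model, subject as a fixed effect, makes the promised adjusted treatment difference non-estimable

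*SAP*

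**What the plan says.** The model is set out in SAP Section 4.3.5, in the text on the EORTC QLQ-C30.

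- **Terms.** "The MMRM model will include patient, treatment, analysis visit, and treatment-by-visit interaction as explanatory variables, the baseline value as a covariate", together with baseline-by-visit. Treatment, visit and their interaction are fixed, and "patient will be treated as a random effect".
- **Output.** "Adjusted mean difference and 95% CIs will be presented to illustrate the effect of treatment".
- **Covariance.** Unstructured, with REML and Kenward-Roger degrees of freedom. If that does not converge, "the following covariance structures will be used in order until convergence is reached": heterogeneous Toeplitz, heterogeneous AR(1), Toeplitz, AR(1).
- **Last step.** If problems remain with the fit or with estimating the treatment effects, "SUBJECT will be treated as a fixed effect".
- **Second use.** The IL52 domain score is modelled "using the same approach described in Section for EORTC QLQ-C30 analysis".

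The trial has parallel groups: "Arm 1 (single agent belantamab mafodotin) will enroll approximately 214 participants and Arm 2 (pom/dex) will enroll approximately 106 participants" (Section 1.2). No cross-over is allowed before the final OS analysis.

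**The concern.** The last step is invoked, among other reasons, when the treatment effect is hard to estimate. Adding one fixed parameter per participant confines the information to comparisons within participants, and neither arm nor baseline varies within a participant. The between-arm difference is thus no longer identified by the model.

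This is the only model-based between-arm comparison that the SAP text at hand gives for Fatigue and IL52, and comparing changes in health-related quality of life between arms is a stated secondary objective. If the step is reached, the team will either have no estimate or will have to choose a replacement model with the data in view. If software prints a treatment coefficient anyway, its value depends on which subjects serve as reference.

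There is also a smaller point of wording. A random patient effect is listed beside an unstructured within-patient matrix. Read literally, one variance parameter is redundant.

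**Working it through.** The SAP gives no figure for this model, so there is none to reproduce. The question is whether the promised contrast is estimable, which depends on the fixed-effects design alone. The covariance structure, REML and Kenward-Roger do not affect it.

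**Inputs.** 214 and 106 participants (Section 1.2) and the fixed terms in Section 4.3.5. The number of visits in the model and the amount of dropout are not stated. I assume 4 or 8 visits, with complete data or with monotone dropout affecting 60% of participants.

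**Algebra.** For participant i in arm t(i) with baseline b_i, at visit j, the mean with subject fixed is

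s_i + v_j + τ_t(i) + (τv)_t(i)j + β b_i + γ_j b_i.

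1. Add any constant c to s_i for everyone in Arm 1 and subtract c from τ_1. No fitted value changes, but the difference between arms shifts by −c at every visit. The data cannot determine it.
2. Add d·b_i to every s_i and subtract d from β. Again no fitted value changes, so the baseline main effect is not identified either.
3. The change in the arm difference between two visits does not involve c. It remains estimable.

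**Rank count.**

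| | 4 visits | 8 visits |
|---|---|---|
| Columns without subject | 1+2+4+8+1+4 = 20 | 1+2+8+16+1+8 = 36 |
| Rank without subject | 8+4 = 12 | 16+8 = 24 |
| Columns with subject | 20+320 = 340 | 36+320 = 356 |
| Rank with subject | 320+3+3+3 = 329 | 320+7+7+7 = 341 |

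The column terms are intercept, treatment, visit, treatment-by-visit, baseline and baseline-by-visit. In the last row the terms are subject, visit, treatment-by-visit and baseline-by-visit; the treatment and baseline main effects add 0.

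**Estimability.** A contrast L is estimable only if L = L(X'X)⁻(X'X).

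- Without subject, the largest discrepancy is 0 for the difference at each visit and averaged over visits, in all scenarios.
- With subject, the discrepancy is 0.010 to 0.011 for the same contrasts. They fail at 4 of 4 and 8 of 8 visits and overall, with or without dropout.
- The change in the difference from first to last visit has discrepancy 0 throughout.
- Averaging the subject effects within each arm does not help (0.0003 to 0.003). The constant c cancels, but the shift in step 2 leaves d times the difference in arm mean baselines.
- If both baseline terms are also removed, the averaged contrast becomes estimable (0), but it is no longer adjusted for baseline.

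**Illustration.** In one simulated data set (4 visits, true difference −5, total SD about 21), eight choices of reference subjects gave the same residual sum of squares, 190,639.944. The treatment coefficients were −64.4, 8.8, 37.9, −70.0, 36.4, 11.4, 65.0 and −8.9. The change in the difference from visit 1 to visit 4 was 2.8146 every time.

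**Random patient effect.** With a random intercept added at 4 visits, covariance parameters against identifiable ones are: unstructured 11/10, heterogeneous Toeplitz 8/8, heterogeneous AR(1) 6/6, Toeplitz 5/4, AR(1) 3/3, compound symmetry 3/2. At 8 visits, unstructured is 37/36. Under the unstructured matrix, with total covariance held constant, intercept variances of 0, 20, 60 and 120 gave the same REML log-likelihood (−4289.387, up to a constant), difference (−2.983) and SE (2.092). The redundancy does not move the treatment estimate.

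**The case against.** The aliasing itself is not in dispute. The case on the other side concerns weight and remedy.

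- **The step is remote.** It comes only after five structures, the last with two covariance parameters, and nothing shows that it is likely to be needed. The analysis is exploratory, the endpoints are supportive, and the descriptive summaries, responder percentages and plots do not use the model. This is right and limits the consequence. It does not make the rule workable.
- **The simulated coefficients overstate the harm.** They come from one data set and from arbitrary coding, and the SAP promises an adjusted difference, not a raw coefficient. A visible failure is more likely than a wrong number. This is fair: the range is only an illustration, and the rank result carries the point.
- **A difference can be recovered.** It can, by averaging subject effects within arm and dropping baseline. But the SAP provides for neither, and the result is not the baseline-adjusted difference that it promises.
- **The random-effect wording may be shorthand.** It may well be, and it is harmless to the estimate under the unstructured matrix. It merits a clarification only.
- **Compound symmetry may not fit where AR(1) failed.** Both have two parameters, a misspecified covariance can bias estimates when data are missing at random, and a robust variance does not correct that. This caution stands, but it applies equally to the AR(1) step that the SAP already accepts.

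**Conclusion.** The concern holds. With subject fixed and the stated terms retained, the adjusted mean difference for Fatigue and IL52 is non-estimable at every visit and overall; only changes in the difference between visits remain. The ranks quoted assume 4 or 8 visits and all 320 planned participants contributing. The aliasing does not depend on those figures, because arm and baseline never vary within a participant.

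The effect is confined to this exploratory model and arises only if the last step is reached. PFS, OS, safety and the descriptive PRO results are unaffected. It should still be corrected, because a pre-specified rule cannot deliver its stated output.

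**What to change.** In Section 4.3.5:

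1. Delete the sentence that makes subject a fixed effect.
2. End the covariance list with a simple structure such as compound symmetry, with a robust variance estimator at that last step if wanted. It would be sensible to add that, if this also fails, only the descriptive results are reported.
3. State that within-patient correlation is modelled through the repeated-measures covariance only, with no separate random patient effect. This matters for compound symmetry too, where a random intercept is again redundant.
4. Apply the same wording to the IL52 model.

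The cost is one sentence deleted, one clarified and a few lines of code. If a robust variance is used, its degrees-of-freedom rule must be stated in place of Kenward-Roger. No new data are needed and no confirmatory analysis changes.

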### ***EORTC QLQ-MY20 and EORTC IL52***

The EORTC Quality of Life Questionnaire 20-item Multiple Myeloma module (QLQ-MY20) is a supplement to the QLQ-C30 instrument used in patients with multiple myeloma [Aronson, 1993; Cocks, 2007]. The module comprises 20 questions that address four myeloma-specific HRQoL domains: Disease Symptoms (EORTC IL52), Side Effects of Treatment, Future Perspective, and Body Image. Three of the four QLQ-MY20 domains are multi-item scales: Disease Symptoms (includes bone aches or pain, back pain, hip pain, arm or shoulder pain, chest pain, and pain increasing with activity); Side Effects of Treatment (includes drowsiness, thirst, feeling ill, dry mouth, hair loss, upset by hair loss, tingling hands or feet, restlessness/agitation, acid indigestion/heartburn, and burning or sore eyes); and Future Perspective (includes worry about death and health in the future, and thinking about illness). The Body Image scale is a single-item scale that addresses physical attractiveness. As with the QLQ-C30, QLQ-MY20 domain scores are averaged and transformed linearly to a score ranging from 0–100. A high score for Disease Symptoms and Side Effects of Treatment represents a high level of symptomatology or problems [Proskorovsky, 2014] (lower score indicates improvement), whereas a high score for Future Perspective and Body Image represents better outcomes (higher score indicates improvement). Details of deriving domain score can be found in Section 6.2.8.2. and more details will be provided in OPS document.

Descriptive summaries (mean, SD, median, min and max) of the actual value and change from baseline at selected time points will be provided for each domain score. The number and percentage of participants with post-baseline score improved by  $\geq 10$ , and  $\geq 5$  points, respectively from baseline score will be summarized at selected time points. Should new thresholds be available at the time of the analysis (ie. from ongoing EORTC group work) these modified thresholds will be used and specified in OPS.

Plots of mean change from baseline (including baseline) and 95% confidence interval over time by visit, and at end of study treatment, last follow-up, and worst case post-baseline for each domain will also be provided. In addition, the plot will also be provided in the subgroup for participants achieving a confirmed partial response (PR) or better based on the investigator-assessed response.

Longitudinal changes from baseline by treatment group for EORTC QLQ-IL52 domain score will be explored using a restricted maximum likelihood-based mixed model for repeated measures (MMRM), using the same approach described in Section for EORTC QLQ-C30 analysis.

**Compliance of PRO-CTCAE, OSDI, EORTC QLQ-C30, EORTC QLQ-MY20 and EORTC QLQ-IL52**

For each of the PROs PRO-CTCAE, OSDI, EORTC QLQ-C30, EORTC QLQ-MY20 and EORTC IL52, overall compliance and compliance by visit will be summarized, based on the following definitions.

[figure not shown]
- Number of patients expected to complete PRO form: Date of study discontinuation and/or date of death will be used to determine the last visit at which a patient is still expected under PRO follow-up.
- Evaluable forms:
  - PRO-CTCAE: with at least one non-missing item score
  - OSDI: with at least one non-missing total score or subscale score
  - EORTC QLQ-C30, EORTC QLQ-MY20: with at least one non-missing scale/domain score
  - EORTC IL52: with non-missing EORTC IL52 scale/domain score

The overall compliance rate is defined as the number of patients with an evaluable baseline form and at least one evaluable post-baseline form, divided by the number of patients expected to complete the baseline form.

Compliance by visit will be calculated as the number of patients with an evaluable form at that visit, divided by the number of patients expected to complete the form at that visit.

**4.4. Exploratory Endpoint(s) Analyses**

CCI

CCI

CCI

CCI

CCI

CCI

CCI

CCI

CCI

## **4.5. Safety Analyses**

The safety analyses will be based on the Safety Analysis Set, unless otherwise specified.

### **4.5.1. Extent of Exposure**

#### **Belantamab mafodotin Arm:**

Extent of exposure to belantamab mafodotin will be summarized.

The number of cycles administered by study treatment will be summarized with mean, median, standard deviation, minimum, and maximum.

The dose intensity (mg/kg/3 weeks), which is calculated as the cumulative actual dose (mg/kg) divided by expected duration of exposure in 3 weeks [(last infusion date – first infusion date+21)/21], will also be summarized. A by subject summary listing of data on exposure to all study treatments will be produced.

The dose intensity (mg/kg/3 weeks) up to a cycle or infusion except the last (cycle or infusion), which is calculated as cumulative actual dose (mg/kg) up to the current cycle, divided by expected duration of exposure up to the current cycle in 3 weeks [(next

infusion date-1 – first infusion date+1)/21], will also be summarized. The dose intensity up to the last cycle or infusion will be calculated in the same way as the dose intensity earlier.

The duration of exposure to study treatment (from first day to last day of treatment) will be calculated and summarized using mean, median, standard deviation, minimum, and maximum. A horizontal bar graph of duration of treatment will be produced that displays duration of treatment in months for each participant.

Dose reductions will be summarized by number of reductions and reasons for reductions. Dose delays will be summarized by number of delays, reasons for the delays, and delay duration (days). The number and percentage of the delays for intervals of 1-21, 22-42 and >42 days will be computed. Primary reasons for dose reductions and dose delays will also be summarized by cycle.

Duration of delays is defined as period from the expected start date of dose to actual start date of current dose. Calculation: (actual start date of current dose - expected start date of dose). Expected start date of dose = actual start date of previous dose + 21.

The summaries of dose modifications will be provided. All the dose reductions, dose escalations, infusion interruptions, incomplete infusions and dose delays will be listed. A plot showing the number and percentage of participants treated at different dose levels over time will be provided.

A patient profile plot will also be produced of all responders (PR or better based on investigator-assessed response) with any dose delays >63 days.

#### **Pomalidomide / Dexamethasone Arm:**

The start date of the overall study treatment is defined as the first dose date of pomalidomide or dexamethasone, whichever is earlier (i.e. the first study drug start date). For pom/dex arm, for each cycle, the cycle start date is defined as the pomalidomide start date; the day before the start date of the current cycle (after the 1st cycle) is defined as the end day of the previous cycle. The end date of the last cycle will be calculated as the earliest of: start date of last treatment cycle + 27 days, treatment discontinuation date, which is the date of the last dose, or the death date if the subject discontinues study or dies before the expected end of the last cycle (start date of last treatment cycle + 27 days).

The overall study treatment end date is defined as the end date of the last cycle. The overall treatment duration (days) is defined as:

Overall treatment duration (days)=the overall study treatment end date – the first study drug start date + 1

Separately for pomalidomide and dexamethasone:

- Duration of treatment = the end date of the last cycle of the study drug – the first dose date of the study drug+1
- Cumulative dose = sum of all actual doses taken across the treatment.

- Dose exposure = total number of days on the study drug during the treatment phase, periods of dose break per protocol or dose interruptions will be excluded
- Average daily dose = cumulative dose / dose exposure (mg/day).
- Dose intensity = cumulative dose / duration of treatment (mg/day).
- Relative dose intensity = dose intensity / plan dose intensity:
  - planned dose intensity for pomalidomide =  $4\text{mg} \times 21/28$  days;
  - planned dose intensity for dexamethasone (for participants  $\leq 75$  years old) =  $40\text{mg} \times 4/28$  days;
  - planned dose intensity for dexamethasone (for participants with  $>75$  years old) =  $20\text{mg} \times 4/28$  days;

Descriptive statistics of cumulative dose, dose exposure, average daily doses, dose intensity and relative dose intensity will be summarized by cycle and by pomalidomide and dexamethasone, separately. The overall summary across cycles will also be provided. Duration of treatment by drug and overall treatment duration will be summarized by descriptive statistics.

The dose modifications (dose reductions, dose interruptions) will be summarized by study drug and listed.

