	
follow-up or end of study, whichever comes first. End of study is defined in Section 5.4 of Protocol Amendment 3. Dose interruptions or reductions may be required following potential drug-associated toxicities.
 
CCI [REDACTED]
 
 
○ For participants who discontinue study treatment for reasons other than PD, disease evaluations will continue to be performed every 3 weeks (<math>\pm 3</math> days) until confirmed (documented) PD, death, start of a new anticancer treatment, withdrawal of consent, or end of the study, whichever occurs first. In case of PD, participants will be followed to ascertain survival status CCI [REDACTED] every 12 weeks (<math>\pm 14</math> days) until withdrawal of consent, lost to follow-up, death or the end of the study.
 
● The final PFS analysis (primary analysis) will be conducted at the time of observing approximately 151 PFS events.
 
● A participant is considered to have completed the study if they are followed until death or end of study.
 
● End of study is defined as when the planned 250 deaths for final OS analysis have occurred, or when all participants have died or are lost to follow up or have withdrawn consent, whichever occurs first. At the first OS interim analysis (~40% OS information fraction), the study will not be stopped regardless of the results. GSK will continue to collect the OS data to conduct the 2nd OS interim analysis to test for efficacy at ~70% OS information fraction. If OS is significant at 70% IF, OS data will continue to be collected until all participants have died, are lost to follow up, or withdrawn consent, or for 2 years after the final OS analysis at 70% IF, whichever occurs first.
 

Study intervention
	
 
● Arm 1: Single agent Belantamab mafodotin. Belantamab mafodotin will be administered intravenously at 2.5 mg/kg on Day 1 (D1) of a Q3W schedule (e.g., 21-day cycle).
 
● Arm 2: Pomalidomide and low-dose dexamethasone (Pom/Dex). Pomalidomide will be administered orally at the approved starting dose of 4 mg daily on Days 1 to 21 of each 28-day cycle, with dexamethasone administered orally at a dose of 40 mg once weekly (Days 1, 8, 15, and 22). For participants over 75 years old, dexamethasone should be administered at the lower dose of 20 mg once weekly (Days 1, 8, 15, and 22).
 

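### The last pom/dex cycle can end at the last dose while planned dose intensity counts 28 days, so a fully dosed participant who has stopped gets a relative dose intensity above 100%

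*SAP*

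**What the plan says.** SAP section 1.2 gives the control schedule. For pomalidomide it reads: "Pomalidomide will be administered orally at the approved starting dose of 4 mg daily on Days 1 to 21 of each 28-day cycle". Dexamethasone is weekly at 40 mg, four doses per cycle with the last on Day 22, and at a lower dose for participants over 75. A participant who takes everything planned therefore has the last pomalidomide dose on Day 21 and the last dexamethasone dose on Day 22 of a 28-day cycle.

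Section 4.5.1 (pom/dex arm) sets the end of the last cycle as the earliest of several dates. One is 27 days after that cycle began. Another is the "treatment discontinuation date, which is the date of the last dose". The final term carries a condition: "or the death date if the subject discontinues study or dies before the expected end of the last cycle". This feeds the denominator: "Duration of treatment = the end date of the last cycle of the study drug" minus that drug's first dose date, plus 1. Then "Dose intensity = cumulative dose / duration of treatment (mg/day"), and relative dose intensity is that figure over a planned value of 4 mg × 21/28 for pomalidomide and 40 mg × 4/28 (or 20 mg × 4/28) for dexamethasone. Results are summarised by cycle and overall.

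Every earlier pom/dex cycle ends on the day before the next one starts, so it keeps its rest days. For belantamab mafodotin, section 4.5.1 defines a dose intensity "which is calculated as the cumulative actual dose (mg/kg) divided by expected duration of exposure in 3 weeks", and that duration adds a full 21 days after the last infusion.

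**The concern.** The planned rate includes the rest days and the observed rate can leave them out of the last cycle. Taken literally, the earliest-of rule picks the last dose whenever treatment has stopped, because Day 21 or 22 always comes before Day 28. The start + 27 limit then never applies to someone who completed the cycle and stopped.

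A reader of the study report would see control-arm relative dose intensity above 100% in participants with no deviation, most of all in those who stopped after few cycles. A genuine reduction can also be offset: it may appear as 100%.

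**Working it through.** **Inputs** (SAP sections 1.2 and 4.5.1). Pomalidomide: 4 mg × 21 = 84 mg per cycle. Dexamethasone: 40 mg × 4 = 160 mg per cycle.

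**Planned dose intensity, reproduced.** Pomalidomide 84/28 = 3.0 mg/day; dexamethasone 160/28 = 5.714 mg/day (80/28 = 2.857 over age 75). The SAP states no expected relative dose intensity.

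**Full dosing over n cycles, then stopped.** Relative dose intensity = (cumulative dose / duration) / planned dose intensity.

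- Last cycle ends on Day 21 (pomalidomide-specific end date): 28n/(28n − 7)
- Last cycle ends on Day 22 (dexamethasone, or one end date for the regimen): 28n/(28n − 6)
- Last cycle ends at start + 27: 28n/28n = 100%

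| Cycles | End on Day 21 | End on Day 22 | End at start + 27 |
|---|---|---|---|
| 1 | 28/21 = 133.3% | 28/22 = 127.3% | 100% |
| 2 | 56/49 = 114.3% | 56/50 = 112.0% | 100% |
| 4 | 112/105 = 106.7% | 112/106 = 105.7% | 100% |
| 12 | 336/329 = 102.1% | 336/330 = 101.8% | 100% |

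The one-cycle row is also what such a participant's last cycle contributes to the by-cycle table, taking the cycle's own length as its denominator: 127-133%.

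**Belantamab mafodotin for comparison.** With n infusions on schedule, the duration is (21(n − 1) + 21)/21 = n three-week units, so on-schedule dosing returns exactly the planned rate.

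**Offsetting a real reduction (illustration).** Full pomalidomide in cycle 1, 75% of the planned amount in cycle 2, last dose on Day 21: (84 + 63)/49 = 3.0 mg/day, or 100%. Over the scheduled 56 days it is 147/56 = 2.625 mg/day, or 87.5%.

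**Stops within a cycle, on-schedule dosing, last dose as end date.**

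- Pomalidomide stopped on Day 7 of cycle 1: (28/7)/3.0 = 133%.
- Dexamethasone stopped in cycle 1: after Day 1, (40/1)/5.714 = 700%; after Day 8, (80/8)/5.714 = 175%; after Day 15, (120/15)/5.714 = 140%.
- Pomalidomide for three full cycles and stopped after Day 7 of cycle 4: 280 mg over 91 days gives (280/91)/3.0 = 102.6%. With a flat start + 27 it would be (280/112)/3.0 = 83.3%. Against the dose planned to the same day it is 280/280 = 100%.

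**The case against.** Several objections have force.

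- **The trailing condition.** The closing condition about leaving the study or dying can be read as governing the last-dose term as well as the death term. Section 1.2 keeps participants in follow-up after treatment stops, so on that reading someone who stops but stays in the study keeps start + 27 and gets 100%. This stands as a possible reading. It narrows who is affected without removing the problem, and it means two programmers could derive different figures from one sentence.
- **Who is affected.** A reader might infer that every fully dosed control participant is inflated. The SAP does not support that: a participant on treatment at cut-off has no discontinuation date and gets start + 27.
- **The size.** 133% at full dosing needs one cycle and a pomalidomide-specific end date. It is also tempting to call 6-7 points the typical error because section 5.2 expects a 4-month control median. That median is a PFS assumption; the SAP gives no expected number of cycles.
- **Time on treatment as a convention.** Dividing by days actually on treatment is defensible in itself, and a flat start + 27 would count a mid-cycle stop as reduced intensity (83.3% above). This stands against the flat rule. It does not rescue the present one, which sets an on-treatment denominator against a planned rate that includes rest days.
- **Masking and comparison of arms.** Cumulative dose, average daily dose, and dose reductions and interruptions are also reported, so a reduction is not hidden from the report as a whole. Nor is there a biased between-arm contrast of relative dose intensity: section 4.5.1 defines that ratio for pom/dex only, and the arms use different units.

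**Conclusion.** The mismatch is real and should be corrected. On the natural reading of section 4.5.1, a control participant who took every planned dose and has stopped gets 127% or 133% after one cycle, 112-114% after two and 106-107% after four, falling towards 100% with more cycles. Stops within a cycle can be misstated by more.

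It is an inconsistency within the section, since earlier pom/dex cycles keep their rest days and the belantamab formula credits the whole last interval. The figures assume on-schedule dosing, 28-day cycles, and that the last-dose term applies to anyone who has stopped treatment. On the narrower reading, only those who leave the study or die are affected. The consequence is confined to descriptive exposure summaries; no hypothesis test or efficacy endpoint uses them.

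**What to change.** For duration of treatment and dose intensity in section 4.5.1:

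- Where the last cycle's planned doses were completed, end it at start + 27 days, or at death if earlier.
- Where treatment stopped within the cycle, compute relative dose intensity as cumulative actual dose divided by the dose planned up to the same end date. Neither rest days nor early stopping then distorts the ratio: both the fully dosed case and the cycle 4 stop above return 100%, and the reduced-dose example returns 87.5%.
- State whether the end date is per drug or per regimen, and what the condition about leaving the study or dying governs.
- State whether the end of pom/dex exposure in section 4.5.3.2 uses the same date. The KVA summaries there take it from section 4.5.1, while belantamab uses last infusion + 20 days, so changing one use alone would leave two control-arm end dates.

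The cost is one derivation change and a few sentences of SAP text. Reported control-arm relative dose intensity becomes somewhat lower.
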